### Adverse reaction (AR)

All untoward and unintended responses to an IMP related to any dose administered.

All adverse events judged by either the reporting investigator or sponsor as having a reasonable suspected causal relationship to an investigational medicinal product are qualified as adverse reactions. The expression reasonable causal relationship means that there is evidence or argument to suggest a causal relationship.

### Multiple signs or symptoms

If an AE consists of several signs or symptoms that can be represented by one single syndrome or diagnosis, the syndrome or diagnosis will be recorded in the CRF as the AE instead of the individual signs or symptoms.

### Worsening

Signs, symptoms, syndromes or diagnoses present before the first administration of the IMP will be considered as AEs if they worsen after the start of the IMP.

### AE rating

The condition of the subjects will be monitored throughout the study. The investigator will collect the AEs reported spontaneously, observed, or elicited in response to a non-leading question (for example, "How have you been feeling since we last asked you?"). The investigator will record all AEs in the source records and the CRF.

The assessment of intensity of an AE will be made using the following general categorical descriptors:

Mild	: Awareness of signs or symptoms, but no disruption of usual activity
Moderate	: Event sufficient to affect usual activity (disturbing)
Severe	: Inability to work or perform usual activities (unacceptable)

The investigator should use clinical judgment in assessing the intensity of events not directly experienced by the subject (e.g., laboratory abnormalities).

The assessment of intensity is outlined in section [8.3](#).

The causal relationship of an AE to the IMP will be rated as follows:

Unrelated	Clearly and incontrovertibly due only to extraneous causes.
Related	There is a reasonable possibility that the IMP may have caused the AE, i.e. the relationship cannot be ruled out. It may include, for example, a temporal relationship, or a pharmacologically-predicted event. Confounding factors, such as concomitant medications, a concurrent illness or relevant medical history, should also be considered.

The action taken with the IMP for an AE will be rated as: product withdrawn, dose not changed, not applicable. AEs requiring therapy will be treated with recognised standards of medical care to protect the health and the well-being of the subject.

The outcome of an AE will be rated as recovered, recovering, not recovered, recovered with sequelae, fatal or unknown. The investigator will follow up any AE until it is resolved or until the medical condition of the subject is stable. All relevant follow-up information will be collected. For AEs that are ongoing at the last visit, the investigator will make thorough efforts to document the outcome.

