## Study Plan

Single doses of MOTREM (LR12) or matching placebo (Part B) are planned to be administered following a sequential group design in 26 healthy young male subjects aged from 18 to 45 years: Part A (Groups 1 and 2 of 1 subject each) followed by Part B (Groups 3 to 8 of 4 subjects each). For Part A (Groups 1 and 2), one subject each will receive MOTREM. For Part B (Groups 3 to 8) 3 subjects will receive MOTREM and 1 subject will receive placebo (3:1 ratio). Dose escalation to the following scheduled dose will only occur after satisfactory review of all safety and tolerability data by the Safety Review Committee in accordance with Table 1, protocol sections [8.2](#) Rules for dose escalation/progression and [8.3](#) Toxicity rules.

Subjects will be screened within 14 days and may be performed over multiple days prior to entering the study on Day -1. Each subject will receive verbal and written information followed by signing of the Informed Consent Form (ICF) prior to any screening procedures taking place. Subjects will be admitted on Day -1 and on Day 1 of the study each subject will receive MOTREM (LR12). All the subjects from Part A (Groups 1 and 2) and Part B (groups 3 to 8) will be discharged on Day 2 after 24h post-dose (start of infusion). They will attend the unit for a follow-up visit on Day 8±1. The End of Study visit will take place on Day 28±2. All the assessments performed during the study are detailed in the Study Plan (Table 2 and Table 3). Study design features as well as number of subjects may be adapted according to Table 1.

The end of study is defined as the last subject, last visit (LSLV).

[figure not shown]

Figure 1: Study Flow Chart.

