**Table 5. Individual Toxicity Rules.**

Individual toxicity rules		
Grade	Severity/Seriousness	Action
I	Mild	No action required
II	Moderate	IMP administration may be continued, amended, temporarily suspended or discontinued in accordance with Investigator's clinical judgement and relevant algorithms for the treatment of toxicities
III	Severe, not serious	IMP administration will be discontinued for the subject
	Severe, serious	IMP administration will be discontinued for the subject
IV	Life-threatening	IMP administration will be discontinued for the subject
V	Fatal	Not Applicable

Standard toxicity grading according to the National Cancer Institute Common Terminology Criteria (NCI CTC) for AEs (NCI CTCAE, version 4.0) will be used to grade the AEs for the purpose of applying the toxicity rules. This is owing to the fact that these are the only standardised set of comprehensive criteria available and have proven useful in healthy volunteer and patient Phase 1 studies. Local laboratory normal values will be applied. Abnormal laboratory and other tests and measurements will be repeated whenever feasible and or appropriate, prior to grading in order to ensure consistency and to exclude technical errors. Diurnal variations in laboratory variables and other measurements as well as baseline status and conditions will be taken into account when assessing whether abnormalities constitute a drug related AE and when grading, if applicable.

The CTCAE displays AE/toxicity Grades I through V with detailed clinical descriptions of severity for individual AEs based on a general guideline. The general grade definitions are described as follows:

Grade I: Mild; asymptomatic or mild symptoms; clinical or diagnostic observations only; intervention not indicated.

Grade II: Moderate; minimal, local or non-invasive intervention indicated; limiting age-appropriate instrumental Activities of Daily Living (ADL)\*.

Grade III: Severe or medically significant but not immediately life-threatening; hospitalisation or prolongation of hospitalisation indicated; disabling; limiting self-care ADL\*\*.

Grade IV: Life-threatening consequences; urgent intervention indicated.

Grade V: Death related to AE.

\*Instrumental ADL refer to preparing meals, shopping for groceries or clothes, using the telephone, managing money, etc.

\*\*Self-care ADL refer to bathing, dressing and undressing, feeding self, using the toilet, taking medications, and not bedridden.

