**Table 11. Daily dose of IMP (MOTREM or matching placebo) for each dose group.**

Dose group	i.v. loading dose T = 15'	Maintenance i.v. dose (mg/kg/h) T = 7h45'	Number of subjects
Group 1	1 mg	-	N = 1
		-	
Group 2	10 mg	-	N = 1
		-	
Group 3	0.5 mg/kg Placebo	0.03 mg/kg/h Placebo	N = 3 N = 1
Group 4	1 mg/kg Placebo	0.1 mg/kg/h Placebo	N = 3 N = 1
Group 5	2 mg/kg Placebo	0.3 mg/kg/h Placebo	N = 3 N = 1
Group 6	5 mg/kg Placebo	1 mg/kg/h Placebo	N = 3 N = 1
Group 7	5 mg/kg Placebo	3 mg/kg/h Placebo	N = 3 N = 1
Group 8	5 mg/kg Placebo	9 mg/kg/h Placebo	N = 3 N = 1

IMOTREM or placebo will be administered by a Research Physician and the details of dosing will be recorded in the CRF. The dosing will be verified by another member of the Investigator's staff.

The study drugs will be dispensed by the pharmacy staff at the clinical study site. The pharmacy staff will be responsible for assembly and labelling of dosing containers according to randomisation schedules and assigned dose level. The amount/ volume of study drug to be administered will be determined based on the assigned dose level for a particular cohort. The procedure for preparing the study drugs and the volume to be prepared for each individual subject dose will be detailed in a Pharmacy Worksheet.

Detailed instructions for dose administration will be included in the Study Operations Manual (SOM).

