### **13.1.2 Recording of Adverse Events and Follow-Up**

All (serious and non-serious) adverse events detected by the Investigator or delegates, or spontaneously notified by the subject at each visit/examination must be reported on the respective section of the CRF.

The following information should be reported for each adverse event, whether or not it can be attributed to trial drug:

- description of adverse event
- date of onset/date of disappearance
- characteristics of the event (seriousness, intensity)
- actions taken (treatment required or dose adjustments must be reported in the CRF)
- outcome
- relationship with trial drug (causality assessment) and/or study participation

**All adverse events must be documented and followed up until the event is either resolved or a satisfactory explanation is found, or the investigator considers it medically justifiable to terminate the follow-up.**

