## **15 STATISTICAL METHODS PLANNED AND DETERMINATION OF SAMPLE SIZE**

### **15.1 Statistical and Analytical Plans**

The analysis will be computed with SAS Version 9.4 (Copyright© 2013 by SAS Institute Inc., Cary, NC, USA).

The statistical analysis plan will be agreed by the sponsor.

Individual data listings will contain all available results. They will be presented by IMP (LR12 vs Placebo), dose group (Group 1-Group 8), subject number and time point if applicable.

Descriptive statistics will be presented by IMP and time point.

All relevant data will be summarised as follows:

- Quantitative endpoints will be presented in terms of mean, standard deviation, median, Q1, Q3, extreme values, number of subjects and missing data.
- Qualitative endpoints will be presented in terms of number and percentage of each modality and number of subjects and missing data.

For quantitative endpoints, Student test for parametric tests or Wilcoxon test for non-parametric tests will be used.

For qualitative endpoints, Chi-square test for parametric tests or Fisher Exact test for non-parametric tests will be used.

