#### **Analysis of treatment-emergent adverse events (TEAE)**

Only TEAE will be summarised and described for the following criteria:

- Number and percentages of subjects with at least one TEAE
- Number and percentages of subjects with at least one severe TEAE
- Number and percentages of subjects with at least one study treatment related TEAE
- Number and percentages of subjects with at least one serious TEAE
- Number and percentages of subjects with at least one TEAE leading to treatment withdrawal

The maximum intensity encountered during the evaluation period will be checked.

The number of TEAE of each category will also be provided by system organ class and preferred term.

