**Reason for Amendment:**

1. The purpose of this amendment is to gather additional pharmacokinetic information. The amendment describes a 100% extension of Group 2 (Part A) in line with the Adaptive feature no 8, Limit I-III. Subject 202 will participate in Part A, group 2 and will be administered an intravenous MOTREM (LR12) dose of 10 mg over 15 min for further evaluation of the pharmacokinetic profile at the selected dose regimen. Three additional pre-dose blood samples will be obtained and processed in accordance with the Adaptive feature no 13 Limit I & II from the volunteer. These changes will not affect the volunteers' safety.

Inotrem SA considers this amendment to be non-substantial.

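### The adverse-event action-taken code has no value for an amended infusion and no clear value for a paused one, although Table 5 permits both and no planned summary counts them

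*Combined protocol and SAP*

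**What the plan says.** Section 13 (AE rating) gives a list of three values with no residual category: "The action taken with the IMP for an AE will be rated as: product withdrawn, dose not changed, not applicable".

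Table 5 (section 8.3) gives the investigator four options for a Grade II event: "IMP administration may be continued, amended, temporarily suspended or discontinued", according to clinical judgement and the relevant algorithms.

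Section 13.1.2 lists what must be reported for each adverse event, including "actions taken (treatment required or dose adjustments must be reported in the CRF".

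Of the TEAE summaries in section 15.1.3, repeated in the synopsis, only one depends on the action taken with the product: "Number and percentages of subjects with at least one TEAE leading to treatment withdrawal". No summary of interrupted or changed infusions is listed.

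Two other provisions bear on the point. Section 10.1.1 says that "the details of dosing will be recorded in the CRF". Section 15.1 says that individual listings hold all available results, ordered by IMP, dose group and subject.

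**The concern.** The rating list is narrower than the set of actions the protocol allows. The primary objective is safety and tolerability, Part B subjects are infused for 8 hours, and section 6.4.2.3 names infusion reactions as a risk. Whether an infusion had to be paused or changed because of an adverse event is direct evidence on tolerability. Under the list as written, that outcome either has to be recorded under a label that does not describe it or drops out of the summaries. Two similar events could also be coded differently.

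**Working it through.** The plan states no figure on this point, so there is none to reproduce. The check compares the passages and then works out what one miscoded subject would do.

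**Step 1: permitted actions against available codes (Grade II, Table 5).**

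| Action permitted | Code in AE rating | Effect on the withdrawal row |
|---|---|---|
| Continued | Dose not changed | None; correct |
| Amended | No truthful code | Raised by one subject if coded withdrawn; otherwise none |
| Temporarily suspended, then resumed | No clear code | Raised by one subject if coded withdrawn; otherwise none |
| Discontinued | Product withdrawn | Counted; correct |

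Two of the four actions are not properly covered. The value *not applicable* does not fill the gap, because an action was taken. The other grades raise no difficulty: Grade I needs no action, Grades III and IV lead to discontinuation, and Table 5 marks Grade V as not applicable.

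**Step 2: do the amendments change this?** Amendment 2 extends Group 2, Amendment 3 alters PK sampling times, and Amendment 4 changes the cohort 8 maintenance dose. None, as shown, touches the code list, the Grade II row of Table 5 or section 13.1.2.

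**Step 3: denominators.**
- Part B: in each group "3 subjects will receive MOTREM and 1 subject will receive placebo (3:1 ratio". With 6 groups, active = 6 × 3 = 18 and placebo = 6 × 1 = 6.
- Part A: 2 groups of 1 active subject, so all planned active = 18 + 2 = 20.
- Amendment 2: "The amendment describes a 100% extension of Group 2 (Part A", which adds 1 subject, so 20 + 1 = 21.

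Section 15.1 says "Descriptive statistics will be presented by IMP and time point" and does not say whether Parts A and B are pooled, so all three active denominators are shown.

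**Step 4: one paused or amended subject coded as withdrawn.** The shift in the withdrawal row is 100 × 1/n percentage points.
- Part B active: 100/18 = 5.6
- All planned active: 100/20 = 5.0
- With the Group 2 extension: 100/21 = 4.8
- If the subject is on placebo: 100/6 = 16.7

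**Step 5: the same subject coded as unchanged or not applicable.** The shift is 0. The withdrawal row stays correct, because a resumed infusion is not a withdrawal, but the event enters no planned summary.

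**The case against.** The strongest reply is that the information is captured elsewhere. Section 13.1.2 calls for dose adjustments in the CRF for each event, section 10.1.1 calls for dosing details, and the listings show everything by subject. With three active subjects per Part B group, a reader of the listings could find each case. This stands: the event is recoverable. It does not remove the gap. Section 13.1.2 does not name a temporary suspension, the dosing record is not said to identify which adverse event led to a pause, and no planned summary draws on either source.

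A second reply is that an infusion paused and then completed in full could truthfully be rated as dose not changed. That also stands, and it is why the paused case is described as having no clear code. An amended infusion has no such answer.

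Third, the e-CRF pages, the Study Operations Manual, the content of the algorithm in Appendix 19.2 and the separate analysis plan mentioned in section 15.1 were not available for this review. They may already offer fuller options. That limits any claim about what will happen, but not the mismatch within the protocol.

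A reader might also infer more than the documents support:
- *That events will be misfiled and the tolerability table will be wrong.* An interruption or amendment must first occur, and only the withdrawn code would distort a planned row.
- *That one miscoded subject moves the row from 0/3 to 1/3, or 33 points.* This needs adverse-event tables by dose group. Section 15.1 plans descriptive statistics by IMP and names dose group only for the listings.
- *That sites will code differently.* The synopsis describes a single-centre study.

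**Conclusion.** The inconsistency between section 13 (AE rating), Table 5 and section 13.1.2 is real, and no amendment shown resolves it. An amended infusion has no truthful code, a paused and resumed one has no clear code, and neither is counted in any planned TEAE summary. The consequence is conditional. If one such event occurs in an active subject and is coded as withdrawn, the withdrawal row is overstated by 4.8 to 5.6 points, depending on the denominator. If it is coded otherwise, that row is right and the event goes uncounted. The figures assume planned group sizes, with or without the one-subject extension of Group 2, and one affected subject. The documents give no event rate. This is a gap in data capture and summary that bears on the primary objective and is cheap to close. It is not a demonstrated error in the tolerability results.

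**What to change.** Reconcile the three passages as follows.

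1. In section 13 (AE rating) and the e-CRF, add two values to the action-taken list: temporarily interrupted, and dose or rate changed.
2. Define product withdrawn, for coding only, as infusion not resumed.
3. In section 15.1.3 and the synopsis, add one row: number and percentage of subjects with at least one TEAE leading to interruption or change of the infusion.

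The clinical choices in Table 5 stay as they are. The change concerns only how an action is recorded and counted. The cost is two extra code values and one extra table row, ideally settled before adverse events are coded.

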## **13.1 Serious Adverse Events (SAE) and Suspected Unexpected Serious Adverse Reaction (SUSAR)**

### **13.1.1 Definitions**

#### Serious Adverse event

Any untoward medical occurrence that at any dose:

- Results in death,
- Is life-threatening,
- Requires inpatient hospitalisation or prolongation of existing hospitalisation,
- Results in persistent or significant disability or incapacity,
- Is a congenital anomaly or birth defect,
- Is an important medical event.

## **Death**

The death of a subject enrolled in a clinical study is *per se* not an event, but an outcome. Any AE resulting in a fatal outcome must be fully documented and reported, including situation for which the death occurred after treatment end, and regardless of the causality relationship between the death and the IMP. The cause of the death is usually the AE. If the cause cannot be determined, the case will be considered an unexplained death.

## **Life-threatening**

Any AE that places the subject, in the view of the initial reporter (investigator), at immediate risk of death from the AE as it occurred, *i.e.* it does not include an AE that, had it occurred in a more severe form, might have caused death.

## **Disability**

A substantial disruption of a person's ability to conduct normal life functions.

## **Important medical event**

An important medical event that may not result in death, be life-threatening, or require hospitalisation may be considered as a SAE when, based upon appropriate medical judgement, it may jeopardise the subject and may require medical or surgical intervention to prevent one of the outcomes listed in the definition. The concept includes AEs which suggest a significant hazard, contraindication or precaution for use, occurrence of malignancy or development of drug dependency or drug abuse.

## **Pregnancy**

Based on the limited reproduction toxicity information, healthy males only will be included.

## **Suspected Unexpected Serious Adverse Reaction**

Suspected unexpected serious adverse reactions (SUSARs) are AEs which have a reasonable possibility to be related to an IMP and are both unexpected (*i.e.* the nature or severity is not expected from the information provided in the investigator's Brochure) and serious. SUSARs are subject to expedited reporting to the national Competent Authority and Ethics Committee.

### **13.1.2 Recording of Adverse Events and Follow-Up**

All (serious and non-serious) adverse events detected by the Investigator or delegates, or spontaneously notified by the subject at each visit/examination must be reported on the respective section of the CRF.

The following information should be reported for each adverse event, whether or not it can be attributed to trial drug:

- description of adverse event
- date of onset/date of disappearance
- characteristics of the event (seriousness, intensity)
- actions taken (treatment required or dose adjustments must be reported in the CRF)
- outcome
- relationship with trial drug (causality assessment) and/or study participation

**All adverse events must be documented and followed up until the event is either resolved or a satisfactory explanation is found, or the investigator considers it medically justifiable to terminate the follow-up.**

**Spontaneously reported SAEs will be collected until 30 days following the final study visit.**

**SAEs experienced after this 30-day period will only be reported if the investigator suspects a causal relationship with the study drug.**

Adverse events (AEs) will be recorded in the CRF throughout the study from day of consent (screening visit) until the last follow up assessment.

Any AEs that are unresolved at the subject's last AE assessment in the study (i.e. at the end of study visit) are to be followed up by the Investigator for as long as medically indicated. INOTREM SA retains the right to request additional information for any subject with ongoing AE(s)/SAE(s) at the end of the study, if judged necessary.

Findings and values related to physical examinations and measurements of ECG, vital signs, (tympanic temperature, blood pressure, and heart rate) and laboratory parameters will be defined as AEs if they are considered clinically relevant deteriorations compared with screening values, as judged by the PI.

### **13.1.3 Reporting of serious adverse events**

If any SAE/SUSAR occurs, the investigator will take appropriate action immediately and will strive to identify the causes of the events.

Any SAE/SUSAR will be notified by the Investigator to For Drug Consulting as soon as possible but not later than 24 hours by e-mail or fax to;

E-mail: [contact]  
[contact]  
[contact]

In addition, the investigator should contact the INOTREM SA Medical Officer.

The initial report will be followed up by a full written report within three working days or five calendar days, whichever comes first unless no further information is available when the follow-up report will be provided as soon as possible when new information becomes available. Further follow-up reports will be provided as and when new information becomes available. Photocopies of results, consultant report(s), a summary of the outcome of the reaction and the Investigator's opinion of IMP relationship to the SAE/SUSAR will accompany the SAE form if and when available.

The Sponsor will also perform an evaluation of the seriousness, causality and expectedness of all SAEs. All SAEs judged by either the Investigator or the Sponsor as having a reasonable suspected causal relationship to an IMP (i.e. definitively, probably or possibly related) will qualify as serious adverse reactions. If the Sponsor disagrees with the Investigator's causality assessment, both the opinion of the Investigator and the Sponsor are provided with the report.

All SAEs will be included in the INOTREM SA pharmacovigilance database.

SUSARs will be notified to the Competent Authority by For Drug Consulting and to the relevant REC within 7 (for fatal and life-threatening SUSARs) or 15 days (all other SUSARs).

Annual safety reporting to the national Competent Authority and the Ethics Committee will be in agreement with ICH guideline E2F "Note for guidance on development safety update reports (DSUR)".

In addition, any other safety issue which may alter the current benefit-risk assessment of the IMP will be reported by the Sponsor (or delegate) on an expedited basis to Health Authorities, Ethics Committees and the Investigator.

The detailed procedure of the SAE/SUSAR reporting will be described in a Safety Management Plan that will be finalised before the start of the study to exactly define the different tasks of the Investigator, the Sponsor and RPL (on behalf of the Sponsor)

